5.1 Study Design

This study aims to utilize both quantitative and qualitative methods to evaluate the combination of our three proposed evidence-based interventions. The study will evaluate three complementary, multi-level interventions for improving the rates of guideline-concordant prostate cancer imaging at VHA. This theory-based strategy was developed based on preliminary data exploring barriers and facilitators to guideline-concordant prostate cancer imaging⁵ subsequently mapped to effective behavior change interventions.^{6,7}

To frame implementation of our intervention at the 10 committed study sites and to inform sustainability and dissemination of our findings, we used the Consolidated Framework for Implementation Research (CFIR), a compilation of existing implementation theories offering an overarching typology to promote implementation theory development and verification about what works in which setting and why. CFIR is composed of 5 domains: Intervention characteristics, Inner Setting, Outer setting, Individuals Involved, and Implementation Process. Each domain has within it between 4 and 12 constructs. The domains and constructs most relevant to the current project include Intervention Characteristics (Evidence Strength & Quality, Trialability, Adaptability, Complexity, and Cost), Inner Setting (Networks, Culture), Outer Setting (Peer Pressure, External Policies), Individuals (Knowledge, Self-Efficacy, Individual stage of change), and Process (Planning, Engaging, Executing, and Evaluating). Qualitative analysis in Aim 2 will use a CFIR-based interview guide to explore participant experience and guide subsequent dissemination.

Using a stepped wedge cluster-randomized design, the first time point will be a baseline measurement, where none of the study sites initiate the intervention. This is a single direction cross-over randomized trial where every site serves, at some point, as both control and an intervention site.⁴ This will allow for an accurate and fair reading of baseline imaging measures at each site. Table 1 shows a chart outlining the proposed project timeline.

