Clinical care cost data will be accessed primarily through the Health Economics Resource Center (HERC) Average Cost File. HERC has created estimates of the cost of all VA health care encounters that have taken place since October 1, 1998. These data are accessible approximately 6-8 months following end of the fiscal year. These data will allow for comparable standardized prices to be applied across all VHA facilities for all follow-up care activities. Cost data will also be obtained from billable private insurance claims. VHA's Medical Care Recovery Program attempts to collect for care performed at VHA when a VA user has private insurance. We will identify subjects in our cohort who have billable private insurance and flag these subjects for exclusion in sensitivity analyses as they may be likely to be more reliant on community care than VA-users without private billable insurance. Preliminary analysis in VISN20 identified that out of a cohort of 260,743 subjects, 17,141 (6.6%) had billable insurance. This variable is available in the CDW.

We will also estimate the cost of implementing the intervention using methods described by Liu et al. in their paper documenting organizational costs for implementing a depression care quality improvement intervention into VHA primary care practices.³⁴ These methods allow for the documentation of organizational costs associated with the implementation effort itself, not just the costs associated with changes in patient care, whose calculation we describe above. We will collect data on participant hours and intervention related activities directly related to the implementation effort. Implementation costs are related to travel, clinical informatics, training sessions, conference calls, development of training materials, email communication, and any other activities spent counseling, training, or supporting personnel at the study sites. Participants will include any individual (provider, study staff, administrator) participating in the implementation project. Data sources used for estimating costs will include interviews, surveys, e-mail communications, project schedules, meeting minutes, project cost records, and government salary information. Costs will be estimated based on length of interviews and surveys, email word count, time of telephone calls, and government travel budgets based on calculated reference ranges for such expenses, as described by Liu et al. 34

Outcomes

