The study's Primary Outcomes determined from the above data sources will be:

Specific Aim 1

- Facility-level utilization of bone scan or abdominal/pelvic CT or abdominal/pelvic MRI among men with newly diagnosed, low-risk prostate cancer. (Inappropriate Imaging)
- Facility-level utilization of bone scan or abdominal/pelvic CT or abdominal/pelvic MRI among men with newly diagnosed, high-risk prostate cancer. (Appropriate Imaging)

Specific Aim 2

- Provider-level utilization of bone scan or abdominal/pelvic CT or abdominal/pelvic MRI among men with newly diagnosed, low-risk prostate cancer. (Inappropriate Imaging)
- Provider-level utilization of bone scan or abdominal/pelvic CT or abdominal/pelvic MRI among men with newly diagnosed, high-risk prostate cancer. (Appropriate Imaging)
- 3. Provider attitudes regarding prostate cancer imaging guidelines and the behavioral intervention

Specific Aim 3

1. Net cost of implementation of physician behavioral intervention VHA. This file will be used to quantify facility-level workforce and imaging technology.

Facility-level descriptors will be obtained from the 2009 VHA Oncology Services Survey.³⁵ As part of the Office of Patient Care Services initiative to conduct systematic program reviews, Oncology Services conducted a survey of cancer care services in VHA.

Missing Data

Missing data has the potential to affect the validity of our results. We foresee 4 potential sources for missing data and propose strategies to deal with them.

- Improper transcription into Oncotrax and CCC: to overcome this, we will train our centrally-located, full-time Research Coordinator to identify missing data fields and search for this information in CAPRI. We expect the study to follow 60 patients from 10 sites per quarter, or a manageable 12 patients per business day.
- 2. Patients seeking care in the private sector through the Veterans Choice Act: Fortunately, when the VA pays for imaging tests, they are indicated in CAPRI. Outside healthcare providers have to send back the statement to collect payment so this information will be manageable to track.³⁶
- 3. Patients seeking care in the private sector through Medicare: [name] found 67% of veterans with an elevated PSA followed up within VHA in the subsequent 24 months.^{37,38} We assume that follow-up will be improved among men with a

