- cancer diagnosis already having chosen to undergo prostate biopsy within VHA. At the completion of the study, we will request CMS records using VIReC's CMS-VA linkage to identify any missing studies performed by a Medicare provider.³⁹
- 4. Patients seeking care in the private sector through private insurance: there is no reliable way to ensure completeness of these data. We will review CAPRI notes for documentation of outside care but may not be able to confirm that none took place. This phenomenon should occur with equal frequency in the control and the intervention sites and should bias our results to the null.

In spite of our best efforts, it is likely that some data will remain missing. The full information maximum likelihood (FIML) method will be used to handle missing data as a less stringent assumption of missing-at-random will be made. Simulation studies have shown that no other missing data handling method performs better than the FIML regardless of the mechanism by which the missing data are generated. 40,41

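### Do scans paid for by private insurance leave the Aim 1 imaging comparison open to a bias that the plan leaves unchecked?

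*Combined protocol and SAP*

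**What the plan says.** Section 5.6, Missing Data, lists four sources of missing data. The fourth is care obtained through private insurance. The plan's remedy is chart review, with a stated limit: "We will review CAPRI notes for documentation of outside care but may not be able to confirm that none took place". The direction of the remaining error is then given: "This phenomenon should occur with equal frequency in the control and the intervention sites and should bias our results to the null". For whatever data are still missing after all these efforts, "The full information maximum likelihood (FIML) method will be used to handle missing data as a less stringent assumption of missing-at-random will be made".

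Earlier in section 5.6, under Cost Analysis, the plan says: "We will identify subjects in our cohort who have billable private insurance and flag these subjects for exclusion in sensitivity analyses". The reason given is that these men may rely more on community care. A preliminary count follows, "out of a cohort of 260,743 subjects, 17,141 (6.6%) had billable insurance", and of the flag itself the plan says "This variable is available in the CDW".

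The Outcomes list, introduced by "Primary Outcomes determined from the above data sources will be", names low-risk and high-risk imaging for Aim 1 but does not mention the flag. Section 5.1 says of the stepped wedge that "every site serves, at some point, as both control and an intervention site".

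**The concern.** Two things look wrong at first reading.

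First, the insurance exclusion is aimed at incomplete capture, which is the problem the Missing Data section admits for the imaging outcomes. Yet it appears under Cost Analysis, names no outcome, and is not picked up under Missing Data. An analyst could run it for Aim 3 only, or decide on Aim 1 after seeing results.

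Second, the direction-of-bias sentence speaks of control and intervention sites, but there are no separate groups of sites. The contrast is each site before and after go-live, adjusted for time, so what matters is whether the captured share of scans changes at crossover. The order check acts on orders placed in CPRS. If it pushed some imaging outside the VA, low-risk imaging would seem to fall more than it did. An unseen scan recorded as no imaging is also a misclassified outcome rather than a blank, so FIML does not repair it.

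At stake would be an overstated H 1.1 result, an understated H 1.2 result, and some loss of power.

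**Working it through.** **Inputs.** From section 5.6: 10 sites; 15 low-risk or 5 high-risk men per site per quarter; low-risk imaging 40% falling to 20%, or to 28.7% in the cautious case; high-risk imaging 66% rising to 86%; coefficient of variation 0.40; two-sided alpha 0.05. The insured share is 17,141/260,743 = 6.57%. That is a share of people in a general VISN20 cohort, not a rate of missed imaging, so its use below is an assumption.

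**Reproducing the plan's power.** I used the Hussey and Hughes variance for the plan's model, with one site crossing per quarter:

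Var = Iσ²(σ² + Tτ²) / [(IU − W)σ² + (U² + ITU − TW − IV)τ²]

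Here I = 10, U = 55, W = V = 385, σ² = p̄(1 − p̄)/N with p̄ the mean of the two rates, and τ = 0.40 × control rate.

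For 40% to 28.7% with a baseline period plus ten steps (T = 11):
- σ² = 0.3435 × 0.6565/15 = 0.01503 and τ² = 0.16² = 0.0256.
- Var = 10 × 0.01503 × (0.01503 + 0.2816) / (165 × 0.01503 + 990 × 0.0256) = 0.0446/27.82 = 0.00160, so SE = 0.0400.
- Power = Φ(0.113/0.0400 − 1.96) = 0.806.

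The same layout gives 0.9993 for 40% to 20% and 0.893 for 66% to 86%. The plan states 0.80, >0.999 and 0.89. With T = 10 the values are 0.776, 0.9987 and 0.869. Ranges below run from T = 10 to T = 11.

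**Equal loss.** If a share c of scans is captured in both conditions, the observed difference is c(p1 − p0). With c = 1 − 0.066 = 0.934:

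| Scenario | True difference | Observed | Power, full capture | Power, c = 0.934 |
|---|---|---|---|---|
| Low-risk 40% to 20% | −0.200 | −0.187 | 0.9987–0.9993 | 0.9974–0.9985 |
| Low-risk 40% to 28.7% | −0.113 | −0.106 | 0.776–0.806 | 0.736–0.767 |
| High-risk 66% to 86% | +0.200 | +0.187 | 0.869–0.893 | 0.778–0.807 |

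This is attenuation, as the plan says. The risk ratio does not move (0.287/0.400 = 0.7175 with or without the factor c), but the plan's model works on the absolute difference. If instead a share f of men is imaged outside at the control rate throughout and all of that is missed, the true and observed differences are both (1 − f)(p1 − p0), and there is no bias on this scale.

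**Unequal loss.** The observed difference is c1·p1 − c0·p0, with c0 before and c1 after go-live.
- c0 = 0.934, c1 = 0.92, 40% to 28.7%: 0.2640 − 0.3736 = −0.110, still short of the true −0.113. Constant capture is therefore sufficient for attenuation but not necessary.
- With 6.6% missed before go-live, the low-risk effect is overstated only once more than 9.2% (28.7% case) or 13.2% (20% case) is missed after it.
- c0 = 1, c1 = 0.934, high-risk: 0.86 × 0.934 − 0.66 = +0.143, again toward the null (power 0.568–0.600).
- c0 = 1, c1 = 0.934, no true low-risk change: 0.40 × (0.934 − 1) = −0.026, SE 0.0426–0.0410, rejection 9.5–9.9% instead of 5%. If half of insured men's scans are lost after go-live, rejection is 6.1–6.2%; if a quarter, 5.3%.

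**What the exclusion buys.** Dropping 6.6% of men leaves 1500 × 0.934 = 1401 low-risk men. Power becomes 0.749–0.780 (28.7% case) and 0.847–0.872 (high-risk). On power it matches the full cohort only once about 67% (low-risk) or 25% (high-risk) of insured men's scans are lost. The plan gives neither fraction.

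**The case for a change.** The best case for a change is that it is cheap. Two sentences and one extra run per outcome, using a variable already held, would settle beforehand whether the exclusion covers the primary outcomes. High-risk power could fall by about 9 points under equal loss, and exclusion would recover most of that. The loss could also be larger: with 15% insured and all their scans missed equally, power is 0.681–0.712 (28.7% case) and 0.661–0.691 (high-risk). A large shift at crossover would do real harm. If the missed share rose from 6.6% to 20%, a null low-risk effect would appear as −5.4 points, with rejection near 27%.

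Part of this stands. The outcomes covered by the exclusion are not named, the equal-loss assumption is asserted without a check, and FIML does not correct unseen scans.

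The rest is weaker. The cost text refers to the cohort generally and to sensitivity analyses in the plural, and its rationale concerns outside care, so nothing confines it to Aim 3. The large-shift figures need a change at go-live that the documents do not suggest: crossover time is randomized and imaging is mostly verified by central chart review. Excluding insured men would not detect such a shift. It also changes the population, so a different estimate could simply reflect different imaging habits. Finally, a sentence saying that attenuation holds only if capture is constant would be false, as the 0.934 and 0.92 example shows.

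**Conclusion.** No change to the plan follows. The Missing Data sentence states equal loss in the two conditions. Since every site passes through both, it can fairly be read as control time against intervention time, and the stated direction of bias is then correct for the absolute difference. The unnamed outcomes are missing detail in a sensitivity analysis that is already planned, and analysts can sensibly fill it by running the exclusion on both Aim 1 outcomes. The primary analysis would be the same either way.

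The plan's power figures and the 6.6% reproduce. Under equal loss at that share, the attenuation is 0.7 points on 11.3 (low-risk) and 1.3 points on 20 (high-risk). Power falls by about 4 and 9 points respectively, and by about 0.1 point in the main low-risk scenario. These sizes assume that 6.6% applies to this cohort and that all insured men's scans are missed; at that share they are upper bounds, because chart notes recover some scans. A bias that created or inflated the low-risk effect would need the missed share to rise at go-live, and the documents give no evidence that it does.

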5.7 Withdrawal of Subjects

Participants will be able to withdrawal any point if they so choose without any consequences. Withdrawal from this study will have no impact on employment at the VA. Enrollment status in this study will remain confidential among personnel involved in the Research team. However, any data collected up to that point may still be utilized.

6.0 Reporting

While this study is less than minimal risk, there is the possibility of loss of data confidentiality. Adverse events and serious adverse events are not likely to occur due to the nature of this intervention. The intervention does not entail greater than minimal risk to either provider participants or their patients. If a reportable event such as an unanticipated problem or protocol deviation should occur among the research team, the PI will be notified immediately. Research staff will record and document all details related to the event. The PI will determine if the event meets criteria to report to IRB, and this decision will be documented, signed, and dated by the PI. In the unlikely event that an adverse event occurs at one of the intervention sites, the Site Research Assistants will report it to the Site PI immediately. The Research Coordinator at each site will be responsible for documenting the details of the event, in addition to contacting the main site research staff. The Site PI will determine if the event meets criteria to report to the IRB. This decision will be documented and the central research study team as well as the main PI will be notified. It is unlikely that findings will reveal results that affect participants' health or welfare in this study. There are no safety conditions that trigger immediate suspension of the research that we anticipate.

7.0 Privacy and Confidentiality

There is minimal risk associated for patients involved with this study. This study will use patient PHI. It is necessary to have access to PHI in order to determine the rates and trends in prostate cancer imaging across the study sites. There is a risk of breach in confidentiality; however, multiple safeguards are in place to ensure information security. Only members of the study team performing data analysis, the Research Coordinator and Project Manager, will have access to central data PHI and patient records. Only the designated member of the LCAC will access the locally generated data reports. A variety of precautions will be taken to ensure the security of patient data. PKI-encrypted email will be used to transmit patient data. PKI is a VA-approved software used to secure the delivery of electronic services to VA employees, contractors, and business partners. PKI-encrypted emails are only accessible to those who have been granted access and are only accessible on the VA network requiring a VA network ID and password. Patient PHI will be stored on password protected, secure sever.

The VA's informatics and computing infrastructure (VINCI) will be used to store and analyze data. Individual investigators and multiple databases may lack sufficient resources to ensure consistency and quality control, or a long-term commitment to data storage and access. Therefore, there are less consistent standards for the protection of Veterans data, data quality, and data access compared to a centralized repository. A centralized research data repository, such as the VA Informatics and Computing Infrastructure (VINCI), offers a number of important advantages: Consistent, defined, and transparent security and standards for access to data; a common point of entry for all investigators who use the data; tools for analysis and reporting; tighter and more consistent control over the standards and quality of the data included; and the ability to standardize and update terminology and format as technology and methodology improve. VINCI is a partnership between the VA Office of Information Technology (OI&T) and the Veterans' Health Administration Office of Research and Development (VHA ORD). VINCI provides the storage and server technologies to securely host suites of databases integrated from select national data. These servers reside at the Austin Information Technology Center (AITC), located in Austin, Texas. To ensure the protection of Veterans data, VINCI maintains compliance with the guidelines set forth by Veterans Health Administration (VHA) Handbook 1200.12, Use of Data and Data Repositories in VHA Research and all other applicable VA and VHA policies and regulations. In addition, VINCI has undergone all security certification activities in support of obtaining an Authorization to Operate (ATO). Access to VINCI resources will be approved in accordance with the requirements of National Data Systems (NDS), VHA Handbook 1200.12, Use of Data and Data Repositories in VHA Research, and all other applicable VA and VHA policies and regulations. Researchers and Operations staff will access the data along with the tools for analysis and reporting in the secure, virtual working environment through a certified VHA network computer using the VA INTRANET (NOTE: VINCI is not accessible through the INTERNET). If not working within a VA or VHA hosted office environment containing VA network access.

researchers may access VINCI through an approved Virtual Private Network (VPN) and Remote Desktop application. The remote computing environment will enable data analysis to be done directly on VINCI-CDW servers located at the Austin Information Technology Center, thus keeping all data from being transmitted to local PC hard drives or servers.

VA REDCap is specifically designed for human subjects research. It is installed and accessibly only on VA network, and login requires VA network ID. The application is also housed on VINCI server. REDCap is a mature, secure web application for building and managing online surveys and databases. The VA REDCap portal is intended to be used by authorized VA network users for viewing and retrieving information only. Each member of the main study site research staff has their own individual passwordprotected account on REDCap that was granted by the VA REDCap support team. It is located explicitly through the VA intranet. This study will have a project file that will be accessible only to authorized REDCap users on this study team at the main research site. VA REDCap login can be accessed at: https://vhacdwweb05.vha.med.va.gov/. Provider privacy will also be maintained. All questionnaires and survey item individual responses will not be shared with any personnel beyond the central research staff. The responses will be directly entered into the secure REDCap project site. Participating providers at each site will have access to their own individual imaging rates in addition to aggregate institution results, through a report created by the data team . The main site Research staff will send the reports through VA outlook email. Participating providers will not be able to view other provider-specific data corresponding with other individual participants. In sites that have more than 3 providers, the Site PI will have access to deidentified individual level rates to improve context, clarity, and goals for the group feedback meetings. Individual participants will receive institutional level data reported as an aggregate, conditional that there are >3 employed providers in the department to be included, in order to protect confidentiality. The Chief of Urology will not be aware of which staff members are enrolled, which study activities have been completed, or the content of individual responses. Identities of participating individuals for in-depth interviews following the intervention will be confidential and will remain within the central study research team in order to feasibly conduct the interview. The data collected will be analyzed and reported as aggregate for reporting of results and future manuscripts. Identities of participants in this portion of the study will not be shared with the Site Pls. Chiefs and other participants will not be aware who has been interviewed (other than themselves, if they chose to participate). Qualitative data reported will retain anonymity of the respondents. The site of the participant will be retained so that the central team members are able to analyze themes among sites by imaging volume (for example, "low imaging sites" versus "high imaging sites"). This information will only be reported as aggregated themes. Participation in this study will not influence or affect employment at VA.

Interviews that have been audio-recorded will be stored on the VA desktop of approved study team. Interviews will be recorded during phone call interviews, and will be recorded by the VA Microsoft Teams application in real time. Microsoft Teams is a

collaboration software that combines chat, meetings, calling, collaboration, application integration, and file storage into a single interface. We will use the application to create a meeting with dial-in information and will record the meeting directly through the application on VA secure desktop. Interviews will be de-identified and uploaded onto the secure NY Harbor research server and will be made available to the VA HSR&D Centralized Transcript Service Program (CTSP), an HSRD-funded initiative for qualitative studies at the VA (PI: [name]). Approved staff from the VA Salt Lake City (VASLC) will transcribe the audio files. The VASLC has a Professional Transcription Service available to VA sites and monitored by their own IRB. The audio recordings to be transcribed by VASLC staff will be labeled by the subject's unique alphanumeric code and saved behind the VA Firewall in the main study site's secure shared project folder. The VASLC transcription staff will be given access to a sub-folder within the study team's secure project folder to be created especially for this exchange. Approved study staff will place a copy of the audio files in this folder for an approved VASLC transcriptionist to access for the purposes of transcription. The VASLC transcriptionist will transcribe each interview verbatim and save the completed transcript in the sub-folder using the same alphanumeric code. No data (audio files, in process transcripts, or completed transcripts) will leave the NY Harbor secure research server. As completed transcripts become available, approved study staff will move these files from the transcription sub-folder into another sub-folder that is only accessible to study staff, where they will be stored and accessed for qualitative analyses. We will collect site information within the demographic questions to be retained for analysis. This will be anonymized when reporting results and will be kept confidential within the NY Harbor research team.

Project research data will only be used by authorized study personnel for the exclusive purposes of this project. PHI or passwords associated with data for this project will never be recorded or shared. Only designated VA research personnel will have access to data stored on VINCI, REDCap, and the secure VA research folder. If an individual is no longer part of the research team, the present study team will submit a modification through Central IRB to remove that individual from the study personnel. All passwords will be changed following a change in personnel, and only shared among authorized study team members via secure communication. The ISO and Privacy Officer will be notified within one hour if improper use or disclosure should occur.

